### **3.3 Criteria of drop out**

- 1) Withdrawal of consent by the participants themselves;
- 2) Procedure converted to open surgery (patients will be followed for intention-to-treat analysis);
- 3) Loss of follow-up (patients may be excluded from per-protocol analysis);
- 4) Ordered to exit by the investigators or attending physicians (occurrence of severe complications or adverse events);
- 5) Cases of unmasked blindness (patients will be excluded from per-protocol analysis);
- 6) Patients who remain intubated after surgery (patients will be excluded from per-protocol analysis).

For drop out cases, the detailed reasons will be recorded and the therapeutic effects recorded in the previous encounter will be regarded as the final results. The Case Report Forms (CRFs) of these cases will be preserved for future reference.

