## 7.3 Postoperative data

- 1) PACU Delirium: Occurrence of delirium in PACU will be assessed using the CAM-ICU 30 mins after extubation and before PACU discharge.
- 2) Postoperative Delirium (POD): POD will be assessed twice daily (8:00-10:00 am, and 18:00-20:00 pm) for 5 days from postoperative day 1 to 5 or until the patient is discharged home if the patient stays in hospital < 5 days. CAM is used for delirium assessment if the patient is on the floor; otherwise, CAM-ICU is used if the patient is in the ICU. Investigators for POD assessment will be trained by a psychiatrist to use CAM and CAM-ICU before the trial is commenced.
- 3) Non-delirium Complications: Any complications occurred within the first 30 days after surgery (for example: cardiac events, cerebrovascular events, renal injury, GI complications, infections, etc.) will be documented. Patients will be assessed via phone call if they are discharged before day 30 after surgery.
- 4) Subjective Pain Score: It will be assessed at PACU and 24 hours after surgery using the Numeric Rating Scale (NRS) (an 11-point scale where 0 indicates no pain and 10 indicates the worst pain).
- 5) Subjective Sleep Quality: It will be assessed at 8:00 am during the first postoperative day using the NRS (an 11-point scale where 0 indicates the best possible sleep and 10 indicates the worst possible sleep).
- 6) Length of Hospital Stay: The readiness for discharge will be used as the last day of hospitalization.
- 7) All-cause 30-day Mortality: Patients or family members will be called for assessment.
- 8) Adverse Events: If an adverse event occurs during patient hospitalization, it will be followed up until its disappearance or therapy ends.

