## 8. Outcome

### 8.1 Primary outcome

Incidence of postoperative delirium during the first 5 days after surgery.

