### **13.3 Patient populations used for analysis**

- 1) The modified intention-to-treat (ITT) population: The modified ITT population includes all patients who undergo randomization, surgery (as long as the skin incision is made), and have the primary outcomes data collected. Patients whose surgery is cancelled or aborted in the middle of surgery (after skin incision) will be included in this population.

The primary outcome is regarded as not collected in the following situations:

- a) death (within postoperative 5 days);
  - b) early hospital discharge (for non-medical reasons and within postoperative 5 days);
  - c) intubated/sedated/comatose for more than 24 hours (within postoperative 5 days);
  - d) withdraw consent (within postoperative 5 days);
  - e) data missing.
- 2) The per-protocol population: The patients from the modified ITT population will be included in the per-protocol population if they fulfill the eligibility, intervention, and outcome assessment specified by the protocol.

The following patients are excluded:

- a) ineligible patients
  - b) randomization allocation error;
  - c) SedLine monitor malfunction (not working at all or >50% of the anesthetic duration (PSI <75) without monitoring data);
  - d) SedLine monitor not blinded in the usual care group;
  - e) being anesthetized with inhalational anesthetics;
  - f) surgery aborted or converted to open.
- 3) As-treated population from the SedLine-guided care group: This population is a subset of the per-protocol population. For patients from the SedLine-guided care group, they are regarded as fulfilling the as-treated criteria if the below-10 SEF AUC (left + right) is less than 10 (or the median value of the AUC, if AUC < 10 gives less than 300 patients). These patients are regarded as having received effective SedLine-guided intervention. This rule does not apply to patients from the per-protocol population from the usual care group.

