## Patient RASS Scores

Location/date	PACU	POD-1		POD-2		POD-3		POD-4		POD-5	
Time		AM	PM								
Score											

**If the RASS score is > -4 (-3 through +4), delirium is assessed using the CAM-ICU Worksheet  
CAM-ICU Worksheet**

Features	Score	Check here if present		
Feature 1: Acute Onset or Fluctuating Course				

Is the patient different than his/her baseline mental status? OR Has the patient had any fluctuation in mental status in the past 24 hours as evidenced by fluctuation on a sedation/level of consciousness scale (i.e., RASS/SAS), GCS, or previous delirium assessment?
	Either question Yes			
Feature 2: Inattention				

Letters Attention Test (See training manual for alternate Pictures) Directions: Say to the patient, “I am going to read you a series of 10 letters. Whenever you hear the letter ‘A,’ indicate by squeezing my hand.” Read letters from the following letter list in a normal tone 3 seconds apart. S A V E A H A A R T or C A S A B L A N C A or A B A D B A D A A Y Errors are counted when patient fails to squeeze on the letter “A” and when the patient squeezes on any letter other than “A.”
	Number of Errors >2			
Feature 3: Altered Level of Consciousness				
Present if the Actual RASS score is anything other than alert and calm (zero)	RASS anything other than zero			
Feature 4: Disorganized Thinking				

Yes/No Questions (Use group A or group B to test, if necessary, group A and B can be used interchangeably)
 
Group A:
 
 
1. Will a stone float on water?
 
2. Are there fish in the sea?
 
3. Does one pound weigh more than two pounds?
 
4. Can you use a hammer to pound a nail?
 
 
Group B:
 
 
1. Will a leaf float on water?
 
2. Are there elephants in the sea?
 
3. Does two pounds weigh more than one pound?
 
4. Can you use a hammer to saw wood?
 
			Combined number of errors >1	

Errors are counted when the patient incorrectly answers a question.			

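### Section 13.3 drops patients from the modified ITT set after four post-randomisation events even when a positive delirium assessment is already recorded, and Section 3.3 points the other way for some of them

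*Combined protocol and SAP*

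**What the plan says.** Section 8.1 defines the primary outcome as "Incidence of postoperative delirium during the first 5 days after surgery". Section 7.3 schedules assessments twice daily on postoperative days 1 to 5, or until an earlier discharge. CAM is used on the ward; "otherwise, CAM-ICU is used if the patient is in the ICU". The worksheet in Supplemental remark 4 sets the threshold for scoring: "If the RASS score is > -4 (-3 through +4), delirium is assessed using the CAM-ICU Worksheet".

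Section 13.3 admits to the modified ITT set patients who were randomised, had a skin incision and had the primary outcome collected. It continues: "The primary outcome is regarded as not collected in the following situations". Items a) to d) are death, early discharge for non-medical reasons, "intubated/sedated/comatose for more than 24 hours (within postoperative 5 days", and withdrawal of consent, each within 5 days. Item e) is missing data. The per-protocol set is drawn from the modified ITT set.

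Section 3.3 lists drop-out cases. They include withdrawal of consent and item 6: "Patients who remain intubated after surgery (patients will be excluded from per-protocol analysis". For drop-outs it states that "the therapeutic effects recorded in the previous encounter will be regarded as the final results". It names no analysis set for that sentence.

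Section 13.2 compares the overall drop-out rate between arms by chi-square test. Section 13.5 names no population for the primary comparison, and 13.3 defines no ITT set other than the modified one.

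**The concern.** The outcome is binary and cumulative: once one assessment on days 1-5 is positive, later events cannot change it. Followed literally, 13.3 still labels that patient's outcome uncollected if one of items a) to d) occurs, and removes the patient. Observed primary events would then leave both numerator and denominator for reasons that arise after randomisation and may be related to delirium.

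Section 3.3 could also be read to keep some of the same patients, so two analysts could build different primary sets from the same data. That choice should not be left until outcomes are known.

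**Working it through.** **1. Does 13.3 reach patients with a recorded positive?** Missing data is its own item, e), so items a) to d) are not confined to patients without data. Item c) shows this best. An ICU patient with RASS from -3 to +4 is scored by CAM-ICU, and that range includes sedated patients. A positive can therefore be recorded before, during or after a qualifying 24 hours. No text exempts it.

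**2. Where do 3.3 and 13.3 overlap?**

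| Situation in 13.3 | Named as drop-out in 3.3? |
|---|---|
| a) death | no |
| b) non-medical early discharge | no |
| c) intubated continuously from surgery for more than 24 h | yes, item 6 (no time threshold; exclusion stated for per-protocol only) |
| c) later re-intubation, or sedation or coma without intubation | no |
| d) withdrawal | yes, item 1 |

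The conflict is limited to the two rows marked yes, and it exists only if the carry-forward sentence covers the primary outcome.

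**3. The plan's own figure.** Section 4.2 gives 14% in controls, a one-third reduction (9.33%), two-sided 0.05 and 80% power. With pooled variance under the null:

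n = [1.960·√(2·0.1167·0.8833) + 0.8416·√(0.14·0.86 + 0.0933·0.9067)]² / 0.0467² = (0.890 + 0.381)² / 0.002178 ≈ 742 per arm, as stated.

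Also 742 × 1.05 ≈ 780. Power at 780 per arm is 0.82. The sample-size arithmetic is not at issue.

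**4. Effect of deleting positives, no true effect.** The documents give no rate for items a) to d), so every share here is an assumption. Let 3.5% of non-delirious patients be excluded in both arms and a share d of positives be deleted. The analysed rate is

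0.14(1 − d) / [0.14(1 − d) + 0.86 × 0.965].

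- EEG arm, d = 10%: 0.126 / 0.9559 = 0.1318
- Control arm, d = 5%: 0.133 / 0.9629 = 0.1381
- RR = 0.1318 / 0.1381 = 0.954
- Exclusions: 780 × (0.014 + 0.0301) = 34.4 versus 780 × (0.007 + 0.0301) = 28.9. Both lie within 5% of 780 (39).

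Type I error comes from simulation (780 per arm, Pearson chi-square, 400,000 trials):

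| Positives deleted, EEG vs control | RR | Type I error |
|---|---|---|
| 2% vs 1% | 0.99 | 0.050 |
| 5% vs 2.5% | 0.98 | 0.054 |
| 10% vs 5% | 0.95 | 0.065 |
| 5% vs 10% | 1.05 | 0.065 |
| 10% vs 10% | 1.00 | 0.050 |

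**5. Planned effect, equal shares deleted.** Power is 0.80, 0.78 and 0.74 when 5%, 10% and 20% of positives are deleted in both arms, against 0.82 with none.

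**6. Does keeping recorded positives suffice?** No. Suppose 10% versus 5% are excluded for reasons unrelated to delirium, with no true effect. The literal rule is then unbiased (type I error 0.050). If all positives are recorded and kept while excluded negatives are dropped, the rates are 0.14 / (0.14 + 0.86 × 0.90) = 0.1532 and 0.14 / (0.14 + 0.86 × 0.95) = 0.1463. That gives RR 1.05 and type I error about 0.065. If onset and exclusion days are spread uniformly over days 1-5 and a positive is recorded only when it precedes exclusion, RR is 1.02 and type I error 0.053.

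**7. Does a life-table with censoring suffice?** Only in part. RR is 1.00 when exclusion is unrelated to delirium or always follows the recorded positive. In the linked 10% versus 5% case with independent onset and exclusion days, RR is about 0.97 and type I error about 0.057, because exclusion before onset is informative.

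**The case against.** The list in 13.3 may have been meant only for patients whose outcome could not be established. The carry-forward sentence in 3.3 speaks loosely of therapeutic effects and could govern other recorded results, leaving 13.3 in charge of the primary outcome. The affected group is probably small: patients are elective, ASA I-III and expected to be extubated, and those unlikely to survive 5 days are excluded. Postoperative assessors are blinded. Section 3.3 records reasons for drop-out, and 13.2 tests for a difference in drop-out between arms. Finally, the literal rule is unbiased when exclusion is unrelated to delirium, whereas keeping positives alone is not.

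Much of this stands. It limits the size of the problem, makes the 3.3 conflict conditional on how that sentence is read, and means the remedy needs a second part. It does not remove the gap. If the narrower intent is right, the text does not say so, and the separate item for missing data points the other way. The comparison in 13.2 can flag an imbalance but does not restore dropped events, and deaths and early discharges are not named as drop-outs in 3.3.

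**Conclusion.** The point holds as a defect in the definition of the primary analysis set. As written, 13.3 drops observed primary events and leaves two rules for withdrawals and for patients intubated from surgery beyond 24 hours. This assumes that the primary comparison uses the modified ITT set, the only ITT set defined, and, for the conflict, that 3.3 covers the primary outcome.

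The size depends on rates the documents do not give. In the scenarios shown, RR under the null ranges from 0.95 to 1.05 and type I error from 0.050 to 0.065. Equal deletion causes no bias under the null and costs power (0.82 to 0.80-0.74 for 5-20% of positives).

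A reader might infer more, in three ways that are not supported:

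- That the rule favours the EEG arm. The documents give no mechanism for unequal deletion, and reversing the shares reverses the bias.
- That 3.3 and 13.3 clash for every listed event. Death, early discharge, later re-intubation, and sedation or coma without intubation are not named in 3.3.
- That a life-table analysis removes all bias. It does so only under the conditions in step 7.

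This should be fixed before analysis. It does not by itself invalidate the trial.

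**What to change.** 1. State in 13.3 that a positive CAM or CAM-ICU recorded on days 1-5 counts as a primary event and keeps the patient in the set. For item c), say that this applies whether the positive came before, during or after the intubated or sedated period. Make it subject to the consent terms on data collected before withdrawal (see 14.2).
2. Because step 1 alone makes inclusion depend on outcome, prespecify with it a sensitivity analysis of all randomised, incised patients. It should also keep those with no positive and incomplete follow-up, by a stated method such as multiple imputation or cumulative incidence to day 5, with a tipping-point check. Treat death as a competing event or report it separately. Do not simply count incomplete patients as non-events.
3. Reconcile the carry-forward sentence in 3.3 with 13.3 so that one rule applies to each patient.

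The cost is wording and one additional analysis. No new data are needed, because the CRF already holds RASS and each delirium assessment. The downsides are a slightly higher observed incidence and a sensitivity analysis that rests on stated assumptions. Step 1 without step 2 can itself bias the comparison (RR 1.02 to 1.05 in the 10% versus 5% unrelated case).

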### **3.4 Criteria of Rejection**

Enrolled cases who meet any of the following criteria will be excluded from further per-protocol analysis.

- 1) Intervention protocol is not executed;
- 2) No or incomplete study record;

Enrolled cases who meet any of the following criteria will be excluded from further as-treated analysis.

Unable to evaluate the effectiveness of intervention (e.g., missing SedLine data).

For rejected cases, the detailed reasons will be recorded and CRFs will be preserved for reference. The results of these cases will be excluded in analysis of therapeutic effects.

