### **6.3 Monitoring**

- 1) All recruited patients from either control or intervention group will receive SedLine EEG monitoring;
- 2) A study coordinator will distribute the monitor 30 mins before the arrival of the patient in the Operating Room;
- 3) The probe of SedLine monitor will be placed on patient's forehead after the patient's arrival in the Operating Room and before the anesthesia induction;
- 4) The monitor data will be collected by the study coordinator.

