### **6.4 Anesthetic care guided by EEG monitoring**

- 1) The monitor screen in the control arm is covered and blinded to the anesthesiologist;
- 2) The monitor in the intervention arm is used by the anesthesiologist to adjust the anesthetic care.
- 3) The goal in the intervention arm is to maintain SEF 10-15 throughout surgery. Avoid burst-suppression.
- 4) In the intervention arm, the anesthesia induction is achieved via propofol pump infusion (slow and controlled). The goal is to avoid burst-suppression and maintain SEF > 10 throughout anesthesia induction.
- 5) The anesthesia maintenance is achieved via the protocol detailed below (6.5). The SedLine-guided intervention protocol is detailed in the **Supplemental remark 1. SedLine-Guided Intervention Flow Chart**.

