## 7.2 Intraoperative data

- 1) Surgical details including type and time of surgery;
- 2) Anesthetic details including the name and dose of any drugs used during surgery;
- 3) The total dose of propofol used for anesthesia induction and maintenance;
- 4) Inputs and outputs including the name and volume of the fluid being administered, the estimated blood loss, the urine output, and any blood products being transfused;
- 5) EEG data including the occurrence, duration and percentage of burst-suppression, SEF and PSI (specific to SedLine monitor).

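### The as-treated rule selects SedLine-arm patients on achieved SEF AUC and leaves usual care unselected, so a comparison of the two would not be protected by randomisation; direction and size of any bias are unknown

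*Combined protocol and SAP*

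**What the plan says.** Section 13.3 defines three populations. Item 3, the as-treated population, is a subset of the per-protocol population. For the SedLine arm, "they are regarded as fulfilling the as-treated criteria if the below-10 SEF AUC (left + right) is less than 10". There is a fallback cut-off: "or the median value of the AUC, if AUC < 10 gives less than 300 patients". Of the patients kept, the plan says: "These patients are regarded as having received effective SedLine-guided intervention". For the other arm: "This rule does not apply to patients from the per-protocol population from the usual care group".

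Section 3.4 foresees an analysis of this population: "Enrolled cases who meet any of the following criteria will be excluded from further as-treated analysis". It adds that rejected cases are left out when therapeutic effects are analysed. Section 13.5 does not say which outcome, test or comparator goes with the as-treated population. It assigns the covariate-adjusted and subgroup analyses to the ITT dataset.

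The EEG exists in both arms. Section 6.3: "All recruited patients from either control or intervention group will receive SedLine EEG monitoring". Section 7.2 lists "EEG data including the occurrence, duration and percentage of burst-suppression, SEF and PSI". Section 6.4 sets the target for the guided arm: "The goal in the intervention arm is to maintain SEF 10-15 throughout surgery".

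**The concern.** The below-10 SEF AUC is measured after randomisation. It may reflect how well guidance was delivered, but also how the patient's own brain responds to anaesthesia. Filtering one arm on it and not the other breaks the balance that randomisation created. If AUC carries prognostic information of its own, the filtered SedLine patients differ in delirium risk from the unfiltered usual-care patients before any effect of guidance is counted.

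The direction depends on the sign of the association. Section 1 links low-frequency EEG activity and burst suppression with more delirium, in cardiac-surgery and ICU settings. That makes a bias towards SedLine plausible. It gives no size and does not concern this AUC.

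At stake is interpretation. Because the plan calls the subset effectively treated, a difference produced by selection could be reported as the effect of properly delivered guidance.

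The fallback is a separate weakness that needs no prognostic assumption: the cut-off is chosen from the observed data, so it can change who counts as effectively treated.

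**Working it through.** **1. The plan's own figure.** Inputs from section 4.2: 14% risk, reduction by one third (to 9.33%), two-sided 0.05, 80% power. With the pooled-variance formula and mean risk 0.1167,

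n = [1.96·√(2·0.1167·0.8833) + 0.8416·√(0.14·0.86 + 0.0933·0.9067)]² / 0.0467² = 741.7, rounded up to 742.

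This agrees with the plan. 742 × 1.05 = 779.1, consistent with the planned 780 per group.

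**2. Null model for the one-sided selection.** From the documents: 14% risk. Assumed: no intervention effect; delirium odds ratio 2.0 per SD of a latent vulnerability V; correlation r between AUC and V; share kept f; 742 per-protocol patients per arm before selection; the section 13.5 chi-square test applied to this comparison.

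- V ~ N(0,1); logit P(delirium) = a + ln(2.0)·V, with a = −1.979 so that overall risk is 14%.
- The AUC score A is standard normal with correlation r to V. SedLine patients are kept if A is in the lowest share f; usual care is not filtered.
- Kept-group risk p = E[P(delirium | V)·Pr(kept | V)] / f, by numerical integration. Null RR = p / 0.14.
- Rejection rate: two-sided pooled z-test, normal approximation.

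Worked case, half kept, r = 0.3: p = 12.12%, so RR = 0.1212/0.14 = 0.866. Pooled risk = (742 × 0.14 + 371 × 0.1212)/1113 = 0.1337. Standard errors are 0.0216 under the test's null and 0.0212 under the model. The difference is 0.0188, and (0.0188 − 1.96 × 0.0216)/0.0212 = −1.11, so 13.3% of trials reject in favour of SedLine. With 0.2% in the other tail the total is 13.5%.

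| Kept | r = 0.1 | r = 0.2 | r = 0.3 | r = 0.5 |
|---|---|---|---|---|
| 50% (371 vs 742) | 0.96; 5.8% | 0.91; 8.5% | 0.87; 13.5% | 0.78; 30.4% |
| 70% (519 vs 742) | 0.97; 5.4% | 0.94; 6.8% | 0.91; 9.3% | 0.85; 18.4% |
| 90% (668 vs 742) | 0.99; 5.1% | 0.98; 5.3% | 0.96; 5.8% | 0.94; 7.7% |

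Each cell is null RR; rejection rate. At r = 0 the result is RR 1.00 and 5.0% throughout. With the sign reversed (r = −0.3, half kept) it is RR 1.13 and 13.8%, now favouring usual care. Over odds ratios 1.5 to 2.5 and r 0.1 to 0.5, half kept spans RR 0.97 to 0.72 (5.3% to 46.3%) and 90% kept spans 0.99 to 0.92 (5.0% to 9.6%). The upper ends need odds ratio 2.5 and r = 0.5 together.

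**3. The fallback.** With 600 or more SedLine per-protocol patients and fewer than 300 under 10, fewer than half are under 10, so the median is at or above 10 and the cut-off can only loosen.

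- 742 patients, 299 under 10: about 371 kept; 371 − 299 = 72 (19%) missed the criterion.
- 742 patients, 200 under 10: about 371 kept; 371 − 200 = 171 (46%) missed it.

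Below 600 patients it can move either way.

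- 500 patients, 200 under 10: about 250 kept; 50 (20%) missed it.
- 500 patients, 280 under 10: about 250 kept, so the cut-off tightens.

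**4. Deleting the fallback alone.** With 299 of 742 kept and r = 0.3 the null RR is 0.84 (15.1% rejections), against 0.87 with 371 kept. The selection remains, and here it is stronger.

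**The case against.** The biased comparison is inferred. No section states an as-treated test, and item 3 is titled as a population from the SedLine-guided group, so a purely within-arm description is possible; then no between-arm bias arises. This stands as a limit. But the sentence exempting usual care does little work unless those patients enter the analysis, and section 3.4 speaks of an as-treated analysis and of therapeutic effects. Between arms remains the likelier reading.

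The size rests on assumed values. This stands too. The calculation shows that bias is possible, not that it is material. Half kept is the fallback case, and an arm titrated to SEF 10-15 may keep most of its patients, where the bias is small.

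Stronger readings are tempting and not supported:

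- A reader might infer that any prognostic AUC favours SedLine. It does so only if higher AUC goes with more delirium.
- A reader might infer that selection alone could reproduce the reduction the trial is powered for. In a two-stratum version with half kept and risk twice as high in the high-AUC half, kept risk is 0.14/(0.5 + 0.5 × 2) = 9.33%, RR 0.67. Nothing in the documents supplies that twofold ratio.
- A reader might infer that the main result is compromised. The rule does not touch the modified ITT primary comparison.

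Nor does section 13.1 offer reassurance in the other direction: its 0.05 threshold is tied to the primary outcome, not to a population, so it would not exclude an as-treated test of delirium.

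**Conclusion.** The concern holds in a conditional form and should be fixed. It is certain that one arm is filtered on a post-randomisation measurement, that the other is expressly exempt, that the fallback cut-off depends on the data, and that the subset is called effectively treated. It is inferred that the subset will be compared with per-protocol usual care. It is conditional that AUC is associated with delirium for reasons other than the guidance; without that there is no bias, and the sign of the association sets its direction.

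The size is unknown. Under the assumptions above it runs from negligible (90% kept, r = 0.1) to substantial (half kept, r = 0.5). The weight is limited because this is a supplementary population: the primary comparison and the ITT-based adjusted and subgroup analyses are unaffected. Confidence is medium, mainly because the comparator is not written down.

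**What to change.** Base no between-arm efficacy conclusion on this one-sided subset. Either:

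- drop the between-arm as-treated comparison and the median fallback together; or
- keep it with a cut-off fixed in advance, the comparator named, the word 'effective' removed, and an explicit exploratory, non-causal label.

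If only a within-arm description is meant, one sentence saying so removes the between-arm problem; the fallback would still need attention.

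In either case, report SEF AUC descriptively in both arms, with its units, and present its association with delirium as an observational analysis. Applying the same cut to both arms is not a general remedy: guidance is meant to change AUC, so patients below the cut need not be comparable across arms.

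The cost is SAP wording plus a descriptive analysis of EEG data already recorded. The downside is that the trial loses, or must caveat, its estimate for effectively treated patients. A compliance-adjusted estimate is optional. Sections 3.4 and 5.2 and the study schedule show that protocol execution was to be tracked, so new data collection is not necessarily required. Whether such an estimate is feasible depends on how execution was recorded, since the intraoperative case report form shows no visible field for whether guidance was followed.
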